4.3 SAFETY ANALYSIS

All safety analyses will be performed using the Safety Population.

4.3.1 Adverse Events

All adverse event reported during the study will be coded using MedDRA version 19.1. All summaries and listings will be presented of the safety population.

Table 15. AE classification

AE classification	Definition
Treatment Emergent Adverse Event (TEAE)	TEAE if: 
• Treatment Start date/time <= AE Start Date/Time <= Date of Last Treatment +1• And• PT not previously reported prior to Treatment• PT reported prior to Treatment however increased in severity after start of treatment
Serious Adverse Event (SAE)	Any event meeting the following criteria: 
• Results in death• Is life-threatening• Requires inpatient hospitalization or prolongation of an existing hospitalization• Results in persistent or significant disability or incapacity• Results in a congenital anomaly or birth defect 
These criteria will be identified by AE Serious criteria = Yes

Patients reporting multiple incidence of an adverse event mapping to the same PT will be counted only once overall, at the most severe severity level, and at the closest relationship to treatment. AEs will be summarized as described in [Table 6](#).

Table 16. Adverse Events

Summaries	Description	Summary Method
Overall Summary	
• TEAEs• Deaths• On-Therapy SAEs• Withdrawals Due to TEAEs (ADOs)	Categorical Summary
TEAEs	
• At Least One AE	
TEAEs By Severity	
• By SOC	
TEAEs By Relationship	
• By PT within SOC	
Listings of All Adverse Event for Patients with: 1. SAEs 2. ADOs 3. Fatal	For Patients meeting the defined criteria, list all all the patients Adverse Events	Data Listing – See Table Shell for variables to include

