8.4.1 Follow-up (Telephone Call)

The Follow-up Telephone Call will occur on Day $36 (\pm 2)$. During this call, participants will be asked to report any AEs since the End of Treatment Visit (Visit 8) and detail any other symptoms or comments they may have.

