10.2 PROCEDURES FOR RECORDING ADVERSE EVENTS

Adverse events will be collected and recorded from the time the participant signs the ICF at the Screening Visit through completion of the Follow-up Telephone Call. All AEs, regardless of the assumption of a causal relationship with study procedures or study drug, must be recorded on the appropriate AE page of the participant's CRF. This record includes AEs the participant reports spontaneously, those observed by the Investigator, and those elicited by the Investigator in response to open-ended questions such as, "Have you had any unusual signs or symptoms since your last visit?" during the study.

Any medical condition that is present when a participant is screened and does not deteriorate in severity and/or frequency should be reported as Medical History and not as an AE. However, if the condition does deteriorate in severity and/or frequency at any time during the study, it should be reported as an AE.

All AEs will be followed until resolution, until the event has stabilised, or until the participant is lost to follow-up.

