11.3.4 Safety Analyses

Adverse events will be coded using the latest version of Medical Dictionary for Regulatory Activities (MedDRA) available at the start of the study. TEAEs are those AEs that started or worsened in severity after the administration of study drug. TEAEs will be summarised by system organ class (SOC) and preferred term (PT) for each treatment group. In addition, listings of severe TEAEs, drug-related AEs, SAEs, AEs leading to study discontinuation, and AEs leading to death (if any) will be provided.

Vital signs and clinical laboratory evaluations at each assessment time point and the change from baseline at each post-dose time point will be summarised for each treatment group.

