3.3 SCHEDULE OF EVALUATIONS

Table 1. Schedule of Evaluations

Schedule of Evaluations									
	Screening Period (14 days)	Pretreatment Period (7 days)		Treatment Period (29±2 days)					Follow-up Period (7±2 days)
Visit Name →	Screening Visit	Pretreatment Visit	Baseline Visit	Randomisation Visit	Day 13 Visit	Day 15 Visit	Day 27 Visit	EOT Visit ^a	Follow-up
Visit Number →	Visit 1	Visit 2	Visit 3	Visit 4	Visit 5	Visit 6	Visit 7	Visit 8	Telephone Call
Visit Day →	Day -21	Day -7	Day -2	Day 1	Day 13±2	Day 15±2	Day 27±2	Day 28±2	Day 36 ± 2
Study Procedure ↓									
Informed consent	X								
Inclusion and exclusion criteria verification	X			X					
Medical and surgical history	X			X					
Rome III status for IBS-C	X								
Physical examination ^b	X			X				X	
Body weight and height ^c	X			X		X		X	
Seated vital signs ^d	X			X		X		X	
Prior and concomitant medicines	X	X	X	X	X	X	X	X	
Clinical laboratory determinations ^e	X								
Pregnancy test ^f	X			X				X	
Completion of HADs and IBS-SSS	X							X	
Laxative, suppository, and enema washout instructions	X								
AE evaluations ^g		X	X	X	X	X	X	X	X
Rescue Medicine dispensed ^h		X		X		X			
Diary training, compliance verification, and reminder ⁱ		X	X		X		X		

Schedule of Evaluations									
	Screening Period (14 days)	Pretreatment Period (7 days)		Treatment Period (29±2 days)					Follow-up Period (7±2 days)
Visit Name →	Screening Visit	Pretreatment Visit	Baseline Visit	Randomisation Visit	Day 13 Visit	Day 15 Visit	Day 27 Visit	EOT Visit ^a	Follow-up
Visit Number →	Visit 1	Visit 2	Visit 3	Visit 4	Visit 5	Visit 6	Visit 7	Visit 8	Telephone Call
Visit Day →	Day -21	Day -7	Day -2	Day 1	Day 13±2	Day 15±2	Day 27±2	Day 28±2	Day 36 ± 2
Study Procedure ↓									
Daily diary recording		X	X	X	X	X	X	X	
Daily diary collection				X		X		X	
Digestive Sensations questionnaire given			X		X		X		
Digestive Sensations questionnaire collected				X		X		X	
AIP fitted ^j			X		X		X		
AIP Assessment				X		X		X	
Randomisation				X					
Study drug dispensed ^k				X					
Study drug accountability						X		X	
Follow-up phone call									X

- a. Participants who are randomised but do not complete the Treatment Period (withdraw consent or are discontinued before they have completed 4 weeks of treatment) shall be considered Treatment-Period withdrawals and should complete the procedures required at the EOT Visit (even if out of window).

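### SAP Table 15 narrows the protocol's TEAE definition in two ways that SAP section 5 does not declare, and its logic for AEs that worsen is ambiguous

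*SAP*

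**What the plan says.** Protocol 11.3.4 (Safety Analyses) gives the definition: "TEAEs are those AEs that started or worsened in severity after the administration of study drug". It sets no end date and no condition on PT. Protocol 10.2 has AEs recorded "from the time the participant signs the ICF at the Screening Visit through completion of the Follow-up Telephone Call", and Protocol 8.4.1 has the caller ask about events since Visit 8.

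SAP 4.3.1, Table 15, sets the onset condition "Treatment Start date/time <= AE Start Date/Time <= Date of Last Treatment +1". The word *And* follows, and then two bullets: "PT not previously reported prior to Treatment" and "PT reported prior to Treatment however increased in severity after start of treatment". No operator is printed between these two bullets.

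SAP Table 16 builds its incidence, severity and relationship tabulations on TEAEs. SAP section 5 lists the departures from the protocol. It cites Protocol 11.3.4 for the laboratory change values but says nothing about the TEAE definition in that same protocol section.

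**The concern.** The same term means different things in the two documents. The AE tables would leave out events that the protocol counts: new events starting more than one day after the last dose, and on-drug recurrences at unchanged severity of a PT reported before dosing. Under one reading, AEs that began before dosing and worsened on drug would also be left out. Most of what the follow-up call is set up to collect would lie outside the TEAE tables.

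SAP section 5 limits efficacy to descriptive statistics after 20 randomised participants, and laboratory tests are taken only at screening, so AEs carry much of the post-dose safety information. If 1:1 allocation gave about 10 per arm (an assumption), one participant omitted from a row moves that incidence by 1/10, about 10 percentage points.

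**Working it through.** The plan gives no figure to reproduce. The check is a day count and a comparison of the rules.

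**Days outside the onset window**

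Inputs: End of Treatment Visit on Day 28 ± 2 (Protocol 8.3.5); follow-up call on Day 36 ± 2 (Protocol 5.1.1.4 and 8.4.1); Follow-up Period of 7 ± 2 days (SAP Table 1). Assumptions: the participant completes treatment, takes the last dose on the day of the End of Treatment Visit, and +1 means one calendar day.

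With last dose on day L and call on day C, the onset days that are collected but excluded number C − (L + 1).

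- Nominal, L = 28 and C = 36: 36 − 29 = 7 days (Days 30 to 36).
- L = 29 (a 29-day Treatment Period), C = 36: 36 − 30 = 6 days.
- Visit windows varied independently: from 34 − 31 = 3 days (L = 30, C = 34) to 38 − 27 = 11 days (L = 26, C = 38).
- Gap from last dose to call held to 7 ± 2 days, so C − L = 5 to 9: from 4 to 8 days.

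These are days, not events.

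**The rules side by side**

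The two PT bullets cannot both be true of one event, so they must be alternatives. That leaves two readings:

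- Reading A: in window AND (new PT OR prior PT with increased severity).
- Reading B: (in window AND new PT) OR prior PT with increased severity.

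With last dose on Day 28:

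| Event | Protocol | SAP, A | SAP, B |
|---|---|---|---|
| New PT, onset Day 10 | TEAE | TEAE | TEAE |
| New PT, onset Day 33 | TEAE | no | no |
| PT reported pre-dose, new episode Day 10, same severity | TEAE | no | no |
| PT reported pre-dose, new record from Day 10, more severe | TEAE | TEAE | TEAE |
| One record from Day −3, worsens Day 10 | TEAE | no | TEAE |
| One record from Day −3, no worsening | no | no | no |

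Rows 2 and 3 differ from the protocol under both readings. These are the two departures. (Under B the cut-off binds new PTs only; under A it binds all onsets.)

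Row 5 depends on the reading and on how the AE is recorded. Entered as a new record at the date of worsening, it becomes row 4 and counts under both. Protocol 10.2 says of a condition present at screening: "if the condition does deteriorate in severity and/or frequency at any time during the study, it should be reported as an AE". For an AE that begins between consent and dosing, neither document says whether worsening opens a new record.

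For the same-PT rule, AEs are collected before dosing for about 7 days if the Screening and Pretreatment Visits coincide, and for up to 14 + 7 = 21 days otherwise.

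**The case against.** The protocol leaves statistical detail to the SAP, and Table 15 prints its definition in full beside the tables that use it, so nothing is concealed. A window tied to the last dose is a legitimate on-treatment choice. The trial stopped after 20 participants, and no primary result depends on this. All of that is fair. But these rules change which events count, which is more than elaboration, and section 5 is where a reader would look for such a change.

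Four stronger readings are tempting, and the documents do not support them.

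- A reader might infer a third departure, that Table 15 definitely excludes pre-dose AEs that worsen. It contains an explicit worsening bullet, bullet nesting may have been lost when the PDF was read, and the recording rule is not stated. This is an ambiguity.
- A reader might turn the excluded days into a share of AEs lost. The last-dose day is assumed, the follow-up length runs from the End of Treatment Visit and not from the last dose, and AEs need not be spread evenly over days.
- A reader might infer that withdrawals due to AEs are materially undercounted. An AE that makes someone stop the drug would normally begin before the last dose, so the cut-off should rarely matter there.
- A reader might infer that the protocol's listings of severe and drug-related AEs were dropped. The listing specifications are in a separate document that was not available.

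**Conclusion.** Two undeclared departures hold under either reading of Table 15: the onset cut-off for new PTs, and the exclusion of same-PT recurrences at unchanged severity. The treatment of worsened pre-dose AEs is unresolved: they are lost only if *And* governs both PT bullets and the AE keeps its pre-dose start date, which would contradict the protocol.

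The size in time is 7 onset days in the nominal case (Days 30 to 36), and 3 to 11 if the visit windows vary independently, resting on the assumed last-dose day. The number of AEs affected and any imbalance between arms cannot be determined from the documents. The effect is confined to the TEAE-based tables. The point is worth correcting but does not bear on the efficacy conclusions.

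**What to change.** Redefine a TEAE in Table 15 as any AE that started or worsened in severity after first dose, through the Follow-up Telephone Call. Print the operator between the two PT bullets if they are kept, and state which start date applies when a pre-dose AE worsens. Keep the last-dose-plus-one window as a labelled on-treatment subset.

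If the sponsor prefers the present definition, the minimum is to declare the differences in section 5, with the logic clarified, and to add a by-arm listing of post-first-dose AEs (new, recurrent or worsened) that Table 15 excludes.

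The cost is SAP wording, one programming condition and one listing, on data already on the CRF. The downside of the wider definition is that a few more off-drug events are counted in both arms; the on-treatment subset keeps them distinguishable.

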To achieve 80% power to detect a difference of 2.2 cm or more (using a simple 2-sided t-test with estimated SD = 2.4 cm and the conventional 5% significance level) in the mean change in abdominal girth (as measured by AIP AUC) from the start to the end of the day, between the active and placebo groups, 20 participants per group (40 participants in all) are required. Assuming a 15% dropout rate, 47 participants would need to be randomised to yield 40 evaluable participants. Estimating a 60% screen/pretreatment failure rate (mostly from failure to meet distension criteria, but also pretreatment abdominal pain and abdominal bloating criteria), 120 participants would need to enter screening to achieve 40 randomised participants.

Analysis Populations:

ITT Population (all who were randomised to a treatment group at the randomisation visit), Safety Population (all randomised participants who received at least one dose of study drug) and Evaluable Population (all participants included in the Safety Population presenting no major protocol deviations with the potential to bias the criteria for evaluation and with full follow-up).

Efficacy Analyses:

Changes from Baseline in abdominal girth at 4 weeks (primary outcome) using analysis of covariance on AUC measures (24-hour AIP) and at 2 weeks as well as changes in maximal abdominal girth at both 2 and 4 weeks.

Change from Baseline in symptom severity and Bristol Stool Form Scale (diary data) using longitudinal regression analysis on weekly average scores.

Change from Baseline in digestive sensation at 2 and 4 weeks as measured by hourly scores, using analyses of covariance on AUC measures.

Safety Analyses:

Adverse events will be summarised by system organ class (SOC), preferred term (PT), and treatment group. Listings will be provided for severe AEs, drug-related AEs, SAEs, and AEs leading to study discontinuation. Descriptive statistics will be calculated on vital signs and clinical laboratory tests by treatment group.

		Sch	edule of 1	Evaluations					
	Screening Period (14 days)	Pretreatmen (7 days	Treatment Period (29±2 days)					Follow-up Period (7± 2 days)	
Visit Name →	Screening Visit	Pretreatment Visit	Baseline Visit	Randomisation Visit	Day 13 Visit	Day 15 Visit	Day 27 Visit	EOT Visit ^a	Follow-up
Visit Number →	Visit 1	Visit 2	Visit 3	Visit 4	Visit 5	Visit 6	Visit 7	Visit 8	Telephone Call
Visit Day →	Day -21	Day -7	Day -2	Day 1	Day 13±2	Day 15±2	Day 27±2	Day 28±2	Day 36 ± 2
Study Procedure ↓									

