10.1.2 Serious Adverse Event

An SAE is defined as any AE occurring at any dose that results in any of the following outcomes:

- Death;
- Life-threatening: the patient was at immediate risk of death from the reaction as it occurred (i.e., it does not include a reaction that hypothetically might have caused death if it had occurred in a more severe form);
- Hospitalisation or prolongation of existing hospitalisation;
- Persistent or significant disability/incapacity: a substantial disruption of a person's ability to conduct normal daily functions;
- Congenital anomaly/birth defect;

• Important medical events: events that may not result in death, be life threatening, or require hospitalisation. Such an event may be considered serious when, based on appropriate medical judgement, it may jeopardise the patient and may require medical or surgical intervention to prevent 1 of the outcomes listed in this definition. Examples of such medical events include allergic bronchospasm requiring intensive treatment in an emergency department or at home, blood dyscrasias or convulsions that do not result in inpatient hospitalisation, or the development of drug dependency or drug abuse.

Clarification should be made between the terms "serious" and "severe" since these 2 terms ARE NOT synonymous. The term "severe" is used to describe the *intensity* (severity) of a specific event (as in mild, moderate, or severe myocardial infarction) (see Section 10.4.1); the event itself, however, may be of relatively minor medical significance (such as a severe headache). "Serious" is based on the patient/event *outcome or action* criteria described above and is usually associated with events that pose a threat to a patient's life or functioning. A **severe** AE does not necessarily need to be considered **serious**. For example, persistent nausea of several hours duration may be considered severe nausea but not an SAE. On the other hand, a stroke resulting in only a minor degree of disability may be considered mild but would be defined as an SAE based on the above noted criteria. Seriousness (not severity) serves as a guide for defining regulatory reporting obligations.

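### SAP Tables 15 and 16 shorten the protocol's SAE definition and omit two promised AE listings, and SAP Section 5 declares neither change

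*SAP*

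**What the plan says.** **Protocol.** Section 10.1.2 gives six criteria for an SAE. The sixth is "Important medical events: events that may not result in death, be life threatening, or require hospitalisation". Section 11.3.4 says that "listings of severe TEAEs, drug-related AEs, SAEs, AEs leading to study discontinuation, and AEs leading to death (if any) will be provided". The synopsis makes the same promise for four of these: "Listings will be provided for severe AEs, drug-related AEs, SAEs, and AEs leading to study discontinuation". Section 10.2 collects AEs from consent to the follow-up telephone call. Section 11.3.4 defines a treatment-emergent AE (TEAE) as one that starts or worsens after study drug is given, with no end date.

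**SAP.** In Section 4.3.1, the SAE criteria in Table 15 stop at the fifth, "Results in a congenital anomaly or birth defect", followed by "These criteria will be identified by AE Serious criteria = Yes". The TEAE window in the same table closes one day after last treatment. Table 16 keeps summary tables, including "TEAEs By Severity" and a matching table by relationship. Its overall summary has a row for "On-Therapy SAEs". Its listings are "Listings of All Adverse Event for Patients with: 1. SAEs 2. ADOs 3. Fatal".

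SAP Section 5 sets out the departures from the protocol in some detail, down to renamed endpoints. The only change it records to the analyses in protocol 11.3.4 is that laboratory change from baseline will not be computed.

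**The concern.** The SAP is meant to carry out the protocol's safety analysis, and Section 5 is where a reader looks for departures. A reader who finds nothing there on AEs will assume that the definitions and listings are unchanged. They are not.

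The listings matter more than usual here. The study stopped after 20 participants were randomised, and the SAP gives descriptive results only. At that size, individual records carry much of the safety information. A table that counts each participant once per preferred term, at worst severity and closest relationship, does not show when an event began, how long it lasted or what was done about it.

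**Working it through.** No sample size, power or error rate enters this point. The check is an item-by-item comparison.

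**Counts**

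| Item | Protocol | SAP | Missing from SAP | Declared in Section 5 |
|---|---|---|---|---|
| SAE criteria | 6 (10.1.2) | 5 (Table 15) | 6 − 5 = 1: important medical events | No |
| AE listings | 5 (11.3.4) | 3 (Table 16) | 5 − 3 = 2: severe TEAEs; drug-related AEs | No |
| End of TEAE window | None (11.3.4) | Last treatment + 1 day (Table 15) | Later onsets | No |

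**Tracing events through both documents**

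In rows 1 to 3 the event is non-serious and the participant has no SAE, ADO or death.

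| Event | Protocol 11.3.4 | SAP Table 16 |
|---|---|---|
| 1. Severe, starts within the SAP window | TEAE summary and severe listing | Counted by SOC, PT and severity; in no named listing |
| 2. Drug-related, starts within the SAP window | TEAE summary and drug-related listing | Counted by SOC, PT and relationship; in no named listing |
| 3. Drug-related, starts after last treatment + 1 | TEAE summary and drug-related listing | In no named output |
| 4. As row 3, but the participant also has an SAE, ADO or death | As row 3 | Listed, because all AEs of such a participant are listed |
| 5. SAE starting in follow-up | SAE listing | Listed; the on-therapy label suggests it is not in the summary count |
| 6. Starts on treatment, first reported at the call | TEAE | TEAE, because the rule uses start date |
| 7. Important medical event flagged serious | SAE listing | Selected by the flag and listed |

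Rows 1 and 2 lose individual detail but keep the count. Row 3 loses both. Rows 4 to 7 are still listed or, for row 6, still tabulated.

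**Length of the period behind row 3**

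Assume that the last dose falls on the day of the End of Treatment Visit, Day 28 ± 2 (protocol 8.3.5), with the call on Day 36 ± 2 (8.4.1). Nominally the window closes on Day 28 + 1 = Day 29, leaving 36 − 29 = 7 days in which AEs are collected but are not TEAEs. With the two windows at opposite extremes the range is 34 − (30 + 1) = 3 days to 38 − (26 + 1) = 11 days.

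**The case against.** The strongest reply is that little information is really lost, and much of it stands.

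- **SAE definition.** A reader might infer that an important medical event would be serious under the protocol and non-serious under the SAP. The documents do not show this. Selection is by a flag in the data, and the SAP has no step for re-judging or downgrading an event. Protocol 10.3 requires SAEs to be recorded on the CRF. Counts change only if the CRF flag was built on the five-item list, and the CRF is not available. SAE reporting during the trial follows protocol Section 10 and is unaffected.
- **Severe and related events.** A reader might infer that these vanish. They do not: both kinds of TEAE stay in the tables by SOC and PT. For participants with an SAE, ADO or death, the SAP listing is wider than the protocol's, since it covers all their AEs.
- **Follow-up SAEs.** The on-therapy row might look like a departure. Protocol 11.3.4 promises a listing of SAEs, not a summary count of all of them, and the SAP keeps that listing without restricting it to on-therapy events.
- **Size from Phase 3.** It is tempting to use the protocol's linaclotide diarrhoea figures (19.8% reported, 5.3% discontinuing) to say how many cases go unlisted. They do not measure this. The listing of AEs leading to discontinuation is in both documents, the protocol describes the diarrhoea as generally mild to moderate, no drug-related share is given, and those trials treated for 12 or 26 weeks, not 4.
- **Separate specification.** SAP Section 3 puts the specifications for tables and listings in another document, which may restore what Table 16 omits. That cannot be excluded. Table 16 does, however, name its listings and refer to the shell only for the variables to include.

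What the reply does not answer is row 3, or the silence of Section 5.

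**Conclusion.** The mismatch is real and undeclared, but its reach is limited.

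- The SAE definition is inconsistent between the documents. An effect on counts is possible but not shown.
- Two of the five promised listings are absent from the SAP. The loss is participant-level detail for participants with no SAE, ADO or death.
- A non-serious AE that starts after last treatment + 1 in such a participant appears in no output the SAP names. The protocol collects it and would summarise it, and would list it if drug-related. The exposed period is about 7 days, with a range of 3 to 11, if the last dose is taken at the End of Treatment Visit.

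These conclusions concern the SAP text. The CRF and the output specification could change the practical result and were not available. This should be corrected before reporting, but it does not put the efficacy results or the reporting of SAEs during the trial in doubt.

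**What to change.** 1. In SAP Table 15, add important medical events, or replace the list with a reference to protocol 10.1.2. Confirm that the CRF serious flag follows the same six criteria.
2. In SAP Table 16, restore the listing of severe TEAEs and the listing of all drug-related AEs, the latter not limited to TEAEs so that it covers onset up to the follow-up call.
3. The protocol's TEAE has no end date and the SAP's does. State in Section 5 that the window was shortened, and say which definition the severe listing uses. The drug-related listing will not pick up late events judged unrelated.
4. If the sponsor prefers to leave out a listing, declare and justify that in Section 5.

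A count of all SAEs through follow-up, with on-therapy SAEs as a sub-row, would be useful but is optional.

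The cost is a few lines of SAP text and two short listings for 20 participants. Severity, causality and the AE records themselves are already required on the CRF (protocol 10.2, 10.4.1 and 10.4.2), so no new data are needed.
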